## **BACKGROUND AND SPECIFIC AIMS**

Coronavirus disease COVID-19 is a highly infectious condition caused by the severe acute respiratory virus coronavirus 2 (SARS-CoV-2). Since the report of the first cases, in Wuhan, China in December 2019, the spread of this virus throughout the world has resulted in a pandemic characterized by high morbidity and mortality and saturation of health care services in nearly all countries. Worldwide, it is estimated that more than 400 million cases have occurred, with more than 6,000,000 deaths. In Puerto Rico, the first case of the disease was identified on March 16, 2020, and since then, a total of 1,139,253 cases have been reported. At least 1 in 579 residents have died from coronavirus, a total of 5,848 deaths by March 2023.

To address the need to generate new information on the impact of COVID-19 and its sequelae among underserved racial and ethnic minority populations, we implemented the Puerto Rico COVID-19 Assessment Study (PR-COAS), sponsored by the Puerto Rico CEAL program, to evaluate the sociodemographic and clinical characteristics, risk factors, outcomes, healthcare utilization, and quality of life of patients after acute infection of COVID-19 and the long-term sequelae among patients receiving services in federally qualified health centers (FQHCs) and community hospitals in Puerto Rico. In addition, we collected information on health care utilization and barriers related to access to care, including testing and vaccination. The Puerto Rico COVID-19 Assessment Study (PR-COAS) successfully established partnership with five FQHCs and the Hospital UPR in Carolina to better characterize the epidemiological and clinical profile of patients with suspected and confirmed COVID-19 infection and to estimate the prevalence of Long COVID in this population. In our first study, we were able to review 2,625 medical records and collect data on the sociodemographic and clinical characteristics of confirmed and suspected COVID-19

patients. We identified a high prevalence of comorbidities among confirmed COVID-19 cases with almost 50% reporting at least one chronic condition, including hypertension (20%), mental health conditions (19%), and diabetes (11%).

Our second study was designed to establish a cohort of Hispanic patients living in Puerto Rico with laboratory-confirmed COVID-19 infection to evaluate the clinical, epidemiological, and risk factors associated with the development of post-COVID-19 sequelae and its impact on the quality of life. Sociodemographic characteristics, comorbidities, vaccination status, persistent or new symptoms after acute infection, healthcare utilization, and quality of life were collected in the initial or follow-up interviews done at 3, 6, 9 and 12 months (in progress). In our preliminary results we found that of 261 patients recruited, 256 had a SARS-CoV-2 infection at least four weeks before the interview. Of these, the mean age was  $48.1 \pm 15.9$  years, 201 (78.8%) were women, and **191 (74.6%) had signs and symptoms compatible with Long-COVID**. Participants with and without Long COVID had a similar mean age, were mainly women, had similar education, and had received their third dose or booster of COVID-19 vaccine. However, participants with Long COVID had a significantly higher prevalence of tiredness, muscle pain, headaches, joint pain, and anxiety than those without Long-COVID. After adjusting for age, sex, and disease severity, **having a chronic condition was significantly associated with higher odds of Long COVID** (OR=3.38; 95% CI=1.62 – 7.04) including asthma (OR=4.78; 95% CI, 1.92 – 11.9), obesity (OR=3.42; 95% CI, 1.64 – 7.13), hypertension (OR=3.04; 95% CI, 1.33 – 6.98), and diabetes (OR=2.76; 95% CI 1.12- 6.77). In addition, we identified a significant impact in the quality of life where those patients living with Long COVID were more likely to report difficulties with daily activities (24% vs. 9%,  $p = 0.01$ ), pain or discomfort (52% vs. 17%,  $p < 0.001$ ), and anxiety or depression symptoms (37% vs. 11%,  $p < 0.001$ ).

[figure not shown]

Figure 1: Prevalence of Long-COVID Symptoms, Puerto Rico COAS

We found a high prevalence of Long-COVID associated with an increased risk among those patients living with comorbidities in Puerto Rico. In addition, our preliminary data suggest that patients with Long COVID and chronic conditions experience a significant impact in their quality of life. Since there is no cure for Long COVID at this moment, patients living with Long COVID could experience symptoms for a long period of time. This might result in challenges for managing their diseases that are similar to those experienced by patients with other chronic illnesses. What are the main challenges and how these patients might benefit from chronic disease self-management interventions to address the impact of Long COVID in their quality of life is still unknown. Therefore, our specific aims are:

### Specific Aim 1:

To evaluate the impact of an evidenced-based intervention for chronic disease self-management in the health-related quality of life (HRQoL) of patients living with Long-COVID in Puerto Rico. To do this we will evaluate the implementation of **“Tomando control de su salud”** (TCS) among patients with Long COVID and chronic diseases participating in the PR-COAS cohort study, and the changes (if any) in data related to HRQoL measures, included data from the baseline and follow up interviews, before and after this implementation. “Tomando control de su salud” is an evidenced based intervention in Spanish and a culturally appropriate version similar to the Chronic Disease Self-Management program of the Centers for Disease Control and Prevention (CDC) aimed to improve disease management skills, including decision-making, problem solving, and action planning among patients with at least one chronic condition.

#### **Specific Aim 2:**

To evaluate the impact of TCS to support chronic disease self-management in patients with Long COVID living in low-income Hispanic communities in Puerto Rico on self-efficacy, disease monitoring, use of health care services, medication use and risk behaviors. To do this we will evaluate the implementation of **“Tomando control de su salud”** (TCS) among patients with Long COVID and chronic diseases participating in the PR-COAS cohort study, and the changes (if any) in data related to measures of chronic diseases management, included data from the baseline interview and follow up interviews before and after this implementation. We will use Kirkpatrick's evaluation model as a framework and guide in analyzing the impact of the TCS program on the participants' self-management of chronic diseases. This model has been widely used for evaluating participants' outcomes in training programs, including research studies aimed to evaluate training programs regarding self-management of chronic health conditions. Like

other chronic diseases self-management related studies that have applied this evaluation model,

, we will use in our study the first three levels of this model as follows:

1. Reaction - At this level, we will evaluate the degree of satisfaction and perception of the participants regarding the TCS program; we will seek to know their opinion and experience about TCS. To do this, we will use data from the TCS program's final survey, titled Formulario Final (Post-Prueba & Evaluación). It includes close-ended questions regarding the TCS sessions' attendance, general satisfaction with the discussed topics and leaders' evaluation, and an open-ended question about the experience participating in the TCS program (the study participants can express their feelings, ideas, opinions, comments or reactions after having participated in the program).
2. Learning - This evaluation level refers to "the degree to which participants acquire the knowledge, skills, attitudes, confidence and commitment expected based on their participation in the learning event". At this second level, we will assess what participants learned from TCS, measuring their progress (if any) and learning attributed to the program in terms of knowledge, skills, attitudes and confidence in managing their chronic health conditions. To do this, we will have a control group and two intervention groups, and we will compare data from the baseline (pre-training) and follow up interviews (post-training), and TCS's initial (Formulario Inicial: Pre-Prueba) and final surveys, before and after the program implementation.
3. Behavior - At this level, we will examine the extent to which TCS program participants are applying what they have learned during the program TCS, as applicable, in terms of self-management of their chronic health conditions. To do this, we will use follow up interviews (3-6 months after program implementation), based on instruments and adapted questions from standardized questionnaires developed and currently used by the Centers for Disease Control and the National Institutes of Health, among others, to evaluate the

impact of TCS program to support chronic disease self-management in patients with Long COVID living on self-efficacy, disease monitoring, use of health care services, medication use, risk behaviors, and health-related quality of life (HRQoL). In addition, we will evaluate the self-management of chronic diseases in patients with Long COVID through the Self-Care of Chronic Illness Inventory V4c, Spanish version. We are going to compare data from the baseline and follow up interviews, and TCS's initial and final surveys, before and after the program implementation, having a control group and two intervention groups.

On the other hand, we will use the Health Belief Model (HBM) as theoretical framework to evaluate the impact of TCS (changes, if any) on the seeking and utilization of healthcare services by adult patients with Long COVID-19 and chronic health conditions, based principally on Agymang-Duah and Rosenberg study (2023). HBM establishes that people adopt appropriate and preventive health behaviors in accordance with core individual factors that can help predict and explain health-related behavioral changes. These essential components of the model are the following:

1. Perceived susceptibility: Beliefs or perceptions of an individual in relation to the possibility that he or she has of becoming ill with a health condition.
2. Perceived severity: Beliefs or perceptions about the severity of a health problem or condition and its possible effects.
3. Perceived benefits: Perceptions about the possible benefits of certain health behaviors.
4. Perceived barriers: Limitations or obstacles perceived by the individual to carry out a certain health action.
5. Cues for action: Factors that motivate the individual to appropriate health action.
6. Self-efficacy: It is the confidence that a person can feel to successfully perform a certain health behavior.

HBM has been used to evaluate the impact of the COVID-19 pandemic on the health service utilization of adult patients with chronic diseases, among other related-aspects.

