## **METHODS**

**Study design:** We propose to conduct a pilot non-randomized-controlled trial to evaluate the impact of “Tomando control de su salud”, an evidenced-based intervention for chronic disease self-management, in the quality of life of patients living with Long-COVID in Puerto Rico.

**Participant selection:** We will invite patients from our cohort study during the 12-month follow-up call. All participants identified with conditions associated with Long COVID or chronic diseases will be invited to participate. These are the inclusion and exclusion criteria:

Inclusion criteria:

- 1) Adult patients 21 years or older
- 2) Participant of PR-COAS cohort that completed the last interview (12-month-follow-up) and authorized to be contacted for further studies.
- 3) Having at least one chronic condition (excluding cancer) diagnosed by a physician or healthcare provider.
- 4) Ability to attend weekly sessions (applicable to intervention group).

Exclusion criteria

- 1) Any clinical or cognitive impairment that limits the participant's ability to decide to participate in the study or complete the interviews.
- 2) Presence of a life threatening or extreme medical condition.

- 3) Planning to move out of the municipality within the next year.

**Sample size determination:** The primary goal of this study is to pilot the potential implementation of this intervention for Long COVID patients. We are therefore not powering for a definitive assessment of the difference between any two groups. However, we expect the preliminary data from this study to provide adequate pilot data from which we will be able to determine the required sample size for a larger scale study. The sample selected will provide an estimate of the effect size and thereby allow preliminary evaluation of the clinical utility associated with the intervention.

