**Sampling strategy:** Participants with Long-COVID and chronic diseases that agree to participate in the intervention will be allocated into one of the study intervention groups that will participate in the “Tomando Control de su Salud” workshops. Those not interested in participating in the intervention will receive general information about chronic disease management available at the CDC website in Spanish, by email, regular postal mail or in person, in addition to their regular health care and will be asked to answer the post questionnaires approximately 3 months after the last interview of the PR-COAS cohort. With an estimated participation rate of about 25 – 30% we expect to identify between 20-25 participants with Long-COVID with at least one-chronic condition. We estimate that about half will be interested in receiving the intervention; therefore, we expect to have about 20-25 participants in the intervention arm divided into two or three workshops of 8 – 12 participants based on the number of patients recruited and about 30-40 participants in the general care group. Figure 2 summarizes the expected recruitment and procedures.

**Proposed intervention:** “Tomando control de su salud” (Spanish Chronic Disease Self-Management)  is a culturally appropriate program developed in Spanish to support Hispanics

patients to build confidence in their ability to manage their health. This intervention was developed by Lorig et al. at Stanford University and has been widely used by the Puerto Rico Department of Health since it is recommended by the CDC as an evidenced-based intervention for chronic disease management.

[figure not shown]

Figure 2: Summary of study recruitment and procedures, PR COAS\_TCS

The intervention consists of small group workshops with 8 to 15 participants lead by two certified trainers, offered virtually or face-to-face (at the EHSRC Office of Clinical and Community Health Research located at the Hospital UPR in Carolina) for 2 1/2 hours once per week for six-week period open to Spanish-speakers with any physical or mental chronic condition or multiple chronic conditions. As part of the intervention, a pre and post TCS assessment will be collected.

Topics included in the training are:

- 1) Healthy eating
- 2) Appropriate exercise for maintaining and improving strength, flexibility, and endurance
- 3) Managing depression
- 4) Appropriate use of medications

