**Data analysis:** Since this is a pilot study the primary focus of the statistical analysis of this study is estimation (effect sizes and associated uncertainty). We will conduct pre- and post-intervention analysis among participants of the intervention group and between group comparisons with intervention and non- intervention groups. Descriptive analyses will be done using frequency distribution and contingency tables for categorical data. Continuous variables will be reported using mean, median, standard deviation, inter-quartile range and range. Chi-square or Fisher's exact test will be done to assess differences in sociodemographic or health indicators between the groups and to compare the independent domains of the quality-of-life scale among patients in the intervention or non-intervention group. To evaluate changes in quality of life before and after the intervention, estimates and 95% confidence intervals will be generated based on the change scores, i.e., using paired data with each subject acting as their own control. Estimates and confidence intervals will be provided for both the individual group changes as well as the difference in change between each pair of groups. We will perform Wilcoxon/Mann-Whitney U-tests (non-parametric) comparing the change scores in each group with each other. These Wilcoxon tests will be performed in addition to a Kruskal-Wallis test (non-parametric ANOVA) in order to test for an overall group effect. The Wilcoxon paired sample test will be used for ordinal data and the Mc Nemar test for significant changes will be used to evaluate dichotomous data. All analyses will be conducted using Stata version 11(Stata Corporation, College Station, Texas, USA).

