## HUMAN SUBJECT PROTECTION

**Consent process:** After the patient expresses interest in participating in the study, study staff will contact the potential participant via phone or face to face to discuss the study informative sheet following the appropriate consent process as described in the method section. The consent process will be done only by the investigators, study staff, or trained interviewers. The study coordinator will oversee the training of the interviewers about the process of consent by the discussion of the informative sheet and the study procedures prior to any contact with potential participants. A script will be developed to explain the process of consent over the phone. The information in the script will include the purpose of the study, duration of subject participation, description of the procedures, risks, benefits, and confidentiality. In addition, it will include information about the voluntary nature of participation and whom to contact for questions. During the process, the subjects will have the opportunity to ask questions, and if the potential participant requests any other information about the study, it will be provided. Although a written consent form will not be collected, the person who will conduct the discussion of the informative sheet should document all the activities, including the date and time of the call, duration, and if there were questions regarding the process. The person in charge of the consent process should also document and certify in a form that the information provided by them is correct and that the subject consented.

Participants will receive an incentive for transportation and/or parking expenses and for the time dedicated for their participation. The intervention group will receive \$25 for each session of the TCS workshop. This incentive will be given to them at the end of each session at the Endowed Health Services Research Center (EHSRC). Upon completion of the final interview, one month after the end of the workshop, the participant will receive a \$25 incentive that can be sent to them by certified mail or can be hand-delivered at the EHSRC office in a specific time scheduled. In the

case of the non-intervention group, participants will receive a \$25 incentive upon completion of the final interview, approximately 3 months after completing the baseline interview, that is, the final PR-COAS interview.

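### The primary goal is to pilot implementation, but attendance and satisfaction are planned only from the end-of-programme form, with no uptake, attendance or completion reported over everyone who agreed to the workshops

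*Combined protocol and SAP*

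**What the plan says.** - **Goal.** METHODS, Sample size determination: "The primary goal of this study is to pilot the potential implementation of this intervention for Long COVID patients". The same paragraph adds "We are therefore not powering for a definitive assessment of the difference between any two groups" and expects the pilot to inform the size of a larger study.
- **Source of attendance and satisfaction.** Specific Aim 2, level 1 (Reaction): "we will use data from the TCS program's final survey, titled Formulario Final (Post-Prueba & Evaluación". The text goes on to list attendance, satisfaction and an open question on experience as content of this form.
- **Nature of the forms.** The outcome measures section describes Form 2, the final form, as self-administered with 40 questions, covering attendance and evaluation. The listed content of Form 1, the initial form, has neither.
- **Timing.** The Proposed intervention paragraph provides one assessment before and one after TCS. The follow-up interview for the intervention group is set one month after TCS is completed.
- **Analysis.** Data analysis: "the primary focus of the statistical analysis of this study is estimation (effect sizes and associated uncertainty". It plans frequency tables, paired change scores and group comparisons. It names no uptake, retention or completion measure and no denominator for attendance.
- **Payment.** Consent process: intervention participants receive $25 per session, and "This incentive will be given to them at the end of each session".

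**The concern.** A pilot of implementation should show how many of those offered the programme take it up, how many sessions they attend and how many finish. Those rates need everyone who agreed to TCS in the denominator. A form filled in at the end of the programme naturally reaches those still attending. The protocol does not say how someone who stops after one or two sessions would receive it, and the follow-up interview has no defined date for a person who never completes.

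The larger study is what is at stake. Its sample size needs a retention rate as well as an effect size. If 20% leave, the number recruited must be multiplied by 1/(1 − 0.20) = 1.25. If 40% leave, the factor is 1/(1 − 0.40) = 1.67. (Both leaving rates are assumed.) As written, the plan does not commit to estimating this rate.

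**Working it through.** **1. The plan's own figures.** There is no attendance, retention or drop-out figure to reproduce. The nearest is the size of the intervention arm: "we expect to have about 20-25 participants in the intervention arm". The inputs in the same paragraph are "we expect to identify between 20-25 participants with Long-COVID with at least one-chronic condition" and "We estimate that about half will be interested in receiving the intervention".

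- Half of 20–25 is 10–12.5, not 20–25.
- Adding the planned general care group of 30–40 gives a total of 50–65. Half of that is 25–32.5.

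Neither range reproduces 20–25. This does not decide the point, but it leaves the expected uptake unclear, which is a further reason to report uptake explicitly.

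**2. Attendance.** Let *d* be the share of those allocated to TCS who leave early and return no Form 2. Let *A* be the mean sessions attended by those who return the form, and *B* the mean for leavers, each out of 6.

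- Attendance from forms = *A*/6
- Attendance over all allocated = [(1 − *d*)*A* + *dB*]/6
- Overstatement = *d*(*A* − *B*)/6

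Assumed values, not in the documents: *A* = 5.5, *B* = 2, *d* from 0 to 40%. With 20 people allocated:

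| Leaving | From forms | All allocated | Overstatement (points) | Completion over all allocated (exact 95% CI) |
|---|---|---|---|---|
| 0% | 91.7% | 91.7% | 0 | 20/20 = 100% (83–100%) |
| 10% | 91.7% | 85.8% | 5.8 | 18/20 = 90% (68–99%) |
| 20% | 91.7% | 80.0% | 11.7 | 16/20 = 80% (56–94%) |
| 30% | 91.7% | 74.2% | 17.5 | 14/20 = 70% (46–88%) |
| 40% | 91.7% | 68.3% | 23.3 | 12/20 = 60% (36–81%) |

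For example, at 20%: 0.20 × (5.5 − 2)/6 = 11.7 points. With 25 allocated and 20% leaving, completion is 20/25 = 80% (59–93%).

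Other assumed attendance values change the size, not the sign. With 5 versus 3 sessions the overstatement is 3.3 to 13.3 points over 10–40% leaving. With 5.5 versus 1 it is 7.5 to 30.0.

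**3. Satisfaction.** Assume 25 allocated, 5 leaving without a form, and 18 of the 20 returned forms satisfied.

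- From forms: 18/20 = 90%
- All allocated, no leaver satisfied: 18/25 = 72%
- All allocated, every leaver satisfied: (18 + 5)/25 = 92%

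The form-based figure lies inside the range 72–92%, so the bias can go either way.

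**The case against.** The strongest reply is that the protocol does not exclude early leavers. No section restricts Form 2 to finishers, and the study keeps phone, email and postal details, so leavers could be reached. Finishers can also report missed sessions or dissatisfaction on the form. The frequency tables in the Data analysis paragraph would cover the form's closed questions. Figure 2, on recruitment and procedures, is not available in the text reviewed and may show participant flow. Both specific aims and the analysis are framed around impact, and Reaction is presented as satisfaction rather than as a feasibility endpoint.

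Much of this stands, and it rules out several stronger readings that a reader might infer:

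- **That leavers are certainly not counted, or that high attendance and satisfaction are built in.** The documents are silent on leavers. Only completion would be 100% automatically, and only if form-returners alone were counted.
- **That satisfaction is inflated.** People may stop for reasons other than dislike, and the direction is open.
- **That an unbiased attendance log already exists.** The protocol describes a payment, not a record. The payment is made at the research centre, while sessions may also be virtual.
- **That early drop-out is the main feasibility risk.** No section says so.
- **That the plan is defective without progression thresholds or a redefined primary outcome.** These are design preferences, and their absence contradicts nothing in the protocol.

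The reply does not supply a denominator. Frequency tables of returned forms describe those who returned them. Having contact details is not a plan to use them.

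**Conclusion.** The point holds in a limited form. The protocol states an implementation goal, names one end-of-programme self-report as its source of attendance and satisfaction, and plans no uptake, attendance or completion over everyone who agreed to TCS. Attendance is at risk of being overstated. Under the main assumptions (5.5 versus 2 of 6 sessions, leavers returning no form) the excess is about 6 to 23 percentage points for 10–40% leaving. It is zero if nobody leaves or if leavers return the form with accurate attendance. Satisfaction would be selective, with unknown direction.

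It would go too far to conclude that feasibility is overstated or that the pilot cannot meet its goal. The first depends on a drop-out rate that the documents do not give. The second takes one reading of a goal that the protocol also ties to estimating effect size for a larger study.

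**What to change.** - **Attendance record.** Record attendance at every session for everyone allocated to TCS, by a sign-in that covers face-to-face and virtual delivery, cross-checked against the $25 session payments. Use this record in place of the Form 2 self-report.
- **Analysis.** Add to the Data analysis paragraph, each with a 95% CI: uptake among those invited; sessions attended out of 6 and completion among all allocated to TCS; and follow-up completeness over all allocated.
- **Satisfaction.** Offer the Form 2 evaluation items to those who stop early, on a voluntary basis because participants may withdraw at any time. Report satisfaction with the number of forms returned out of all allocated, and give bounds that count non-returners first as all not satisfied and then as all satisfied.

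The cost is some protocol wording, a sign-in sheet for six sessions and 20–25 people, and a few contacts with those who stop. The downside is that reported attendance may look less favourable. The change is best made before the workshops start, since attendance not recorded at the time is hard to recover.

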The last interview of the cohort study (PR-COAS) in which the participants will be identified, which collect information on general aspects of self-care of chronic diseases, healthcare utilization, vaccination status, lifestyles modifications, and health-related quality of life among others, will be used as baseline for the purposes of this study. In addition, a follow up interview will be coordinated one month after completing TCS for the intervention group and approximately 3 months after the last interview of the cohort study for the control group. The following indicators will be collected: Health care services utilization (primary care, emergency room and hospitalizations), compliance with prescribed medications, risk behaviors (such as smoking, physical activity, alcohol use), nutritional awareness, self-efficacy for disease management based on the level of confidence) and quality of life. The standard data collected by the PRDOH for this intervention (*Formulario 1: Formulario Inicial, Preprueba, and Formulario 2: Formulario Final, Post-Prueba & Evaluación, Rev. Enero 2022*) will also be used for analysis. The Form 1 is a self-administered questionnaire of 28 closed-ended questions that collects TCS participants' sociodemographic and contact information (name, municipality of residence, marital status, education, age, sex, medical plan, email), general information on diagnosed health chronic conditions, COVID-19 vaccination, level of confidence in managing chronic conditions, general health, use of health services, and lifestyles (e.g. consumption of vegetables, fruits and alcoholic beverages, physical activity and whether or not you smoke). The Form 2 is a 40-question self-administered questionnaire that mainly collects general information about the lifestyles of TCS workshop participants (consumption of vegetables, fruits and alcoholic beverages, physical activity and whether or not they smoke), general health status, level of confidence in managing health chronic conditions, utilization of health services, attendance, evaluation and experience in TCS workshop.

The impact of health-related quality of life will be assessed using the following scales:

- EQ-5D-5L (Spanish version), which includes five dimensions: mobility, self-care, daily activities, pain or discomfort, and anxiety or depression.
- Fatigue (NIH PROMIS® Neuro-QoL Item Bank v1.0, Short Form, Spanish version)

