**TABLE 2: PROPOSED TIMELINE**

		9 - Months								
Proposed Activities		1	2	3	4	5	6	7	8	9
Intervention for Long-COVID – chronic disease self-management	Training or recruitment of trainers for “Tomando Control de su Salud” intervention	X	X							
	Submission and approval of IRB		X	X						
	Participant selection and group allocation				X	X	X			
	Intervention workshops (8 – 12 participants)							X	X	
	3-month follow-up interview								X	X
	Data analysis and dissemination							X	X	X

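### Aim 2 places the Behavior assessment 3–6 months after the programme, but the only interview scheduled for the TCS group is one month after completion and the nine-month timeline cannot hold a 3–6-month one

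*Combined protocol and SAP*

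**What the plan says.** The combined protocol and SAP gives the timing of post-programme follow-up in four places.

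- **Specific Aim 2, level 3 (Behavior).** The purpose is stated as "we will examine the extent to which TCS program participants are applying what they have learned during the program TCS". For the timing: "we will use follow up interviews (3-6 months after program implementation").
- **Methods, Outcome measures.** For the intervention group, "a follow up interview will be coordinated one month after completing TCS for the intervention group". For the controls, the interview comes "approximately 3 months after the last interview of the cohort study for the control group". That last cohort (PR-COAS) interview "will be used as baseline for the purposes of this study".
- **Human Subject Protection, Consent process.** The last payment to the intervention group is tied to one contact: "Upon completion of the final interview, one month after the end of the workshop".
- **Table 2.** Participant selection is in months 4–6, workshops in months 7–8, and a "3-month follow-up interview" in months 8–9. Month 9 is the last month. The table does not say what the three months are counted from.

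The workshop itself is one session a week for six weeks (Methods, Proposed intervention).

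**The concern.** The Methods and the consent section agree on one interview, one month after TCS. Specific Aim 2 describes a later one. No other source in the documents could supply it. The last cohort interview is already used as baseline, and the programme's own final form is a self-administered survey, not a later interview.

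Level 3 covers self-care, self-efficacy, service use, medication use, risk behaviours and quality of life. Data taken at one month describe early application of what was taught. If they were reported under the Aim 2 description, the follow-up time would be misstated.

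This matters even in a pilot. The Data analysis section makes estimation the main focus, and the sample size section says the results will inform the size of a larger study. An effect size attached to the wrong follow-up time would misinform that design. Staff who schedule interviews would also be working from conflicting text.

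**Working it through.** There is no power or sample-size figure to reproduce. The plan's figure to be tested is the 3–6-month interval, and the check is calendar arithmetic.

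**Inputs**
- Workshops in months 7–8, timeline of 9 months (Table 2). Month *m* is read as elapsed time *m* − 1 to *m*, so workshops lie between 6.0 and 8.0 and the study ends at 9.0.
- Six weekly sessions (Methods). First to last session is 5 weeks; six full weeks is the longer reading. Both are carried.
- Conversion: 365.25 / 12 / 7 = 4.35 weeks per month. So 5 weeks = 1.15 months and 6 weeks = 1.38 months.
- Scheduled interview: programme end + 1 month (Methods; Consent process).

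**Room after the programme ends** (9.0 − programme end)
- Earliest workshop: end = 6.0 + 1.15 = 7.15, or 6.0 + 1.38 = 7.38. Room = 9.0 − 7.15 = 1.85, or 9.0 − 7.38 = 1.62 months.
- Latest workshop: end = 8.0. Room = 1.0 month.

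**Does the scheduled interview fit?** It falls between 7.15 + 1 = 8.15 and 8.0 + 1 = 9.0, so yes.

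**Where would 3–6 months after completion fall?**
- Three months: 10.15–10.38 (earliest workshop) to 11.0 (latest).
- Six months: 13.15–13.38 (earliest) to 14.0 (latest).
- These dates are 1.15 to 5.0 months past the end of the timeline.

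**If the interval is counted from the first session instead**
- Scheduled interview: 1.15 + 1 = 2.15, or 1.38 + 1 = 2.38 months. Still under three.
- The most the timeline allows: 9.0 − 6.0 = 3.0 months, for a workshop starting on the first day of month 7 and an interview on the last day of month 9.
- Latest workshop: start = 8.0 − 1.15 = 6.85, or 8.0 − 1.38 = 6.62. Room = 2.15 or 2.38 months.
- Six months: 12.0 at the earliest, which is outside the study.

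**If the Table 2 label is counted from baseline.** Assume baseline is taken during the participant-selection months, elapsed 3.0–6.0. The TCS interview at 8.15–9.0 then falls between 8.15 − 6.0 = 2.15 and 9.0 − 3.0 = 6.0 months after baseline. The label can therefore be read as time since baseline. It cannot mean three months after programme end, because the row stops at 9.0 and that date is never earlier than 10.15.

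**The case against.** The strongest defence is that this is an inconsistency of wording in a pilot that makes no definitive claim. The behaviour measures are all in the scheduled follow-up interview, and the Data analysis section compares scores before and after without naming a 3–6-month interval. Much of that stands. A reader might infer that the Behavior evaluation has no data behind it; the documents do not support that. Only the stated time is wrong.

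Four further points on that side also stand.

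- **Table 2 may not conflict.** It is tempting to count its label as a third, contradictory follow-up time. The three-month figure elsewhere belongs to the controls and is counted from the last cohort interview, so the row may mean time since baseline. It is undefined, not shown to be contradictory.
- **The one-month interview fits.** A reader might infer that late workshops push it past month 9. Table 2 already ends workshops by the close of month 8, so it falls at 9.0 at the latest. No extra rule on start dates is needed.
- **Sustained change is not promised.** The protocol speaks of applying what was learned.
- **One time point for everyone would be wrong.** Controls have no programme end, and the Behavior level compares them with the intervention groups.

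The defence does not remove the core point. Aim 2 counts from programme implementation and refers to programme participants, so neither a baseline origin nor the control schedule explains its interval.

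**Conclusion.** The Behavior level of Aim 2 claims a follow-up time that the design does not have. The intervention group is interviewed one month after completion, against 3–6 months stated. Within the timeline the interval after completion cannot exceed about 1.6–1.9 months for the earliest workshop, or 1.0 month for the latest. If programme implementation is taken to mean the first session, the scheduled interview is at about 2.2–2.4 months; three months is reached only at the extreme edge of the timeline, and six not at all.

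The conclusion rests on Table 2 being followed as printed and on a programme length of five to six weeks. It does not depend on which of those lengths is used. The baseline reading of the Table 2 label depends on the assumption that baseline falls in months 4–6, but the conclusion about Aim 2 does not.

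**What to change.** 1. In Specific Aim 2, level 3, replace the 3–6-month interval with the scheduled timing for each group: intervention, one month after completing TCS; control, about three months after the last PR-COAS interview.
2. Relabel the follow-up row of Table 2 in the same way, so that each group's starting point is explicit.
3. State that the Behavior conclusion, and any effect size carried into a larger trial, refers to short-term change about one month after the programme.

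This costs wording only, but the claim becomes less favourable. The alternative is to keep a 3–6-month claim, extend the timeline and add a later interview. Counted from completion, that means running to between about month 10.2 (three months, earliest workshop) and month 14.0 (six months, latest workshop), plus one more contact per participant.
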